9.2.3.2.3. Safety specification

For the following elements in the safety specification, subjects who experienced a relevant event will be listed in tabular form:

- VAED and VAERD

Definition: Any event coded as one of the following PTs:

Vaccine associated enhanced respiratory disease, Vaccine associated enhanced disease, Dyspnoea, Tachypnoea, Hypoxia, COVID-19 pneumonia, Respiratory failure, Acute respiratory distress syndrome, Cardiac failure, Cardiogenic shock, Acute myocardial infarction, Arrhythmia, Myocarditis, Vomiting, Diarrhoea, Abdominal pain, Jaundice, Acute hepatic failure, Deep vein thrombosis, Pulmonary embolism, Peripheral ischaemia, Vasculitis, Shock, Acute kidney injury, Renal failure, Altered state of consciousness, Seizure, Encephalopathy, Meningitis, Cerebrovascular accident, Thrombocytopenia, Disseminated intravascular coagulation, Chilblains, Erythema multiforme, Multiple organ dysfunction syndrome, Multisystem inflammatory syndrome in children

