#### **8.2.2. Exclusion criteria**

There are no exclusion criteria for this study.

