1. REVISION HISTORY

| Version/ Date/ Author(s)/ Status of Study | Summary of Changes/Comments |
|--|---|
| 1.0 23-MAR-2021 PPD Before Enrollment | First edition |
| 2.0 04-AUG-2021 PPD Ongoing | 
Section 3
 
 Deleted some descriptions to allow for interim analyses that will be performed for purposes other than the periodic safety reporting. |
| | 
Section 7, Section 9.2.3.1.2
 
 Corrections of typographical or minor errors; unification of terms with the protocol |
| | 
Section 9.2.2.1
 
 Modified the age categorization to align with the summarization in the interim report of the Investigation of Health Status of Recipients Vaccinated First conducted by the Sciences Research Group of the Ministry of Health, Labour and Welfare. |
| 3.0 13-DEC-2021 PPD Ongoing | 
Section 2.1
 
 Deleted the categories for duration of safety assessment. |
| | 
Section 2.1, Section 2.2, Section 5.4, Section 9.2.3.1.3, Section 10
 
 Made changes in accordance with the protocol revision concerning subjects with booster vaccination. |
| | 
Section 5.4
 
 Added subgroups for presence/absence of suspected pregnancy/ of lactation (in accordance with the Investigation of Health Status of Recipients Vaccinated First) Deleted the plan to summarize subjects for presence/absence of pregnancy and of lactation per safety assessment period, in association with the deletion of the duration categories. |
| | 
Section 9.2.1.1
 
 Corrected what subjects should be included in the analyses for tabulation. |

| Version/ Date/ Author(s)/ Status of Study | Summary of Changes/Comments |
|--|---|
| | 
Section 9.2.2.1
 
 Added summarization items in accordance with the subgroups defined. Added summarization of data for presence/absence of allergy Added summarization items concerning initial immunization and booster vaccination. |
| | 
Section 9.2.3.1.1
 
 Deleted unnecessary analysis plans. Deleted the plan to summarize relevant subjects for each category of duration of safety assessment, in association with the deletion of the duration categories. |

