| | 
Section 10
 
 Updated to include lists of subjects in the scope of the safety specification (Section 9.2.3.2.3) and of subjects included in additional subgroups (Section 9.2.3.4). Updated to include a listing of subjects who received one dose of vaccination for the initial immunization during the Investigation of Health Status of Recipients Vaccinated First and received a second dose during the observation period of this study |

| Version/ Date/ Author(s)/ Status of Study | Summary of Changes/Comments |
|--|--|
| 5.0 09-NOV-2022 PPD All data fixed | 
Section 8
 
 Added how to handle the data lacking information on date. Changed the name of the tabulated list. |
| | 
Section 9.2.2.1
 
 Added “unknown” as a category for summarization of presence/absence of booster (third) vaccination. |
| | 
Section 9.2.3.2.1
 
 Editorial revisions |
| | 
Section 9.2.3.2.2
 
 Added the analysis plan for onset time of serious adverse events. |
| | 
Section 10
 
 Added a list of information about COVID-19 in subjects who experienced serious adverse events (COVID-19) Changed the name of a list to “Excluded data in subjects lacking information on booster (third) vaccination” (Section 8) Added a list of “Details of reason for discontinuation in subjects who discontinued before booster (third) vaccination” |

| Version/ Date/ Author(s)/ Status of Study | Summary of Changes/Comments |
|--|---|
| 6.0 05-DEC-2022 PPD All data fixed | 
Section 9
 
 Added a statement that data collected from the Investigation of Health Status of Recipients Vaccinated First will be reviewed according to Pfizer's coding rules, and how the data will be handled in the analysis. |
| | 
Section 9.2.3.2.3
 
 Changed the MedDRA version to 25.1 for PTs. |
| | 
Section 11.1
 
 Deleted the title of the figure. |

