2.2. Study Objective

In this investigation, the healthcare professionals who are vaccinated with this product early after the marketing approval of this product (participants in the Investigation of Health Status of Recipients Vaccinated First conducted by the Science Research Group of the Ministry of Health, Labour and Welfare) will be followed for 11 months from the day following 28 days after the final vaccination of the initial immunization with this product (end date of observation period in Investigation of Health Status of Recipients Vaccinated First) to 12 months after the final vaccination of the initial immunization with this product, information on serious adverse events and COVID19 observed during the follow-up period will be collected.

If booster vaccination isn't conducted, the long-term safety after the initial immunization of this product during the follow-up period will be assessed.

In booster vaccination is conducted, the long-term safety after the initial immunization of this product up to the day before booster vaccination will be confirmed, and information on serious adverse events and COVID-19 will continuously obtained after booster vaccination.

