2.3. Safety Specifications**2.3.1. Important potential risks**

Important potential risks include vaccine-associated enhanced disease (VAED) and vaccine-associated enhanced respiratory disease (VAERD).

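### The only multisystem inflammatory term defining the VAED/VAERD listing is worded for children, so an adult case in this healthcare-professional cohort could be left off it

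*SAP*

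**What the plan says.** SAP 9.2.3.2.3 plans a tabular list of subjects with a VAED or VAERD event and fixes the case definition by coded term: "Definition: Any event coded as one of the following PTs". The closed list ends with "Multiple organ dysfunction syndrome, Multisystem inflammatory syndrome in children". Its last entry, "Multisystem inflammatory syndrome in children", is the only multisystem inflammatory term on it. Section 10 of the SAP repeats the output as a separate list of VAED/VAERD subjects and refers back to 9.2.3.2.3 for the definition.

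SAP 2.3.1 and Protocol 7.1 name VAED/VAERD as an important potential risk, and no other important potential risk is named. SAP 2.2 describes the cohort as "the healthcare professionals who are vaccinated with this product early after the marketing approval of this product". The dictionary version appears in the SAP revision history under version 6.0: "Changed the MedDRA version to 25.1 for PTs".

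**The concern.** Including a multisystem inflammatory syndrome term shows that the sponsor judged the syndrome relevant to the risk. The form chosen, however, describes an age group that a cohort of healthcare professionals is not expected to contain. Because matching is on the exact PT, an adult or age-neutral form of the same syndrome does not qualify.

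At stake is the completeness of the only output dedicated to this risk. The SAP plans no VAED/VAERD count, proportion or comparison, so the PT list alone decides who is shown. The listing is meant to bring out individual rare cases, and a reader who relies on it would not see a case that the list fails to name.

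**Working it through.** The plan gives no figure to reproduce, and no power or precision calculation bears on the point. The check is a count of the list, a reading of the population text, and a trace of how a case would flow through the outputs.

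**1. The list (SAP 9.2.3.2.3).** Split at the commas, it has 36 entries, all distinct.
- Entries containing *inflammatory*: 1 of 36, the paediatric term.
- Entries containing *child*: 1 of 36, the same term.
- Entries containing *adult*: 0 of 36.

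**2. Other routes into the definition.** SAP 9.2.3.2.3 states no grouped query, wildcard or medical review step. SAP 6.1 says that events in scope of the safety specification are specified separately, and 9.2.3.2.3 is the only such specification in the two documents.

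**3. The population.** The protocol title, Protocol 7 and SAP 2.2 all describe healthcare professionals. No age criterion is set, and Protocol 8.2.2 states: "There are no exclusion criteria for this study". The age bands in SAP 9.2.2.1 start at 0 years, but the revision history explains the banding by consistency with the preceding investigation: "Modified the age categorization to align with the summarization in the interim report of the Investigation of Health Status of Recipients Vaccinated First". The text on minors in Protocol 9.2 is conditional. An adult cohort is therefore the sensible reading, but it is inferred from occupation.

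**4. Tracing an adult case.**

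| How the case is coded | On the VAED/VAERD listing? |
|---|---|
| To the listed paediatric PT | Yes |
| To an adult or age-neutral PT, plus a listed component as a separate event (such as Myocarditis, Shock or Acute kidney injury) | Yes, through the component |
| To an adult or age-neutral PT only | No: 0 of 36 PTs match |

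In the third row, a serious case still appears in the table by system organ class and PT (SAP 9.2.3.2.1), in the onset-time table if it occurred before any booster (SAP 9.2.3.2.2), and in the section 10 listing of subjects with serious adverse events. None of these labels it as VAED/VAERD.

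**5. Size.** Each case in the third row leaves the listing one subject short. With the planned maximum of 20,000 subjects (Protocol 8.5.1), one case is 1/20,000 = 0.005% of the cohort. The documents give no rate from which to say how many such cases to expect; zero is possible, in which case the listing is unchanged. SAP 4 rules out hypothesis tests, and the VAED/VAERD definition feeds no proportion, risk ratio or denominator.

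**The case against.** The strongest objection is that the point depends on a dictionary that is not in the documents. It matters only if MedDRA 25.1 holds an adult or age-neutral PT and an adult case would be coded there and not to the listed term. The documents show neither. This stands, and it is why the remedy begins with a look-up. It does not remove the mismatch between the term's wording and the cohort, which is visible in the SAP itself.

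A reader might go further and infer that the paediatric entry can never match in this study and so has no sensitivity at all. The documents do not support that. There is no age criterion, and the coding conventions are not given.

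A reader might also infer that an adult case would go unseen. That is not supported either. A serious case reaches the outputs named in the working above. Under Protocol 10.1 it must also be reported to the sponsor's safety group within 24 hours, with detailed follow-up. A separately coded listed component would bring the subject onto the VAED/VAERD listing as well.

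Finally, SAP version 6.0 is marked as written with all data fixed, so adding a term now changes a safety definition after the fact. That is a fair cost. Open labelling of the addition deals with it, and no inference depends on the listing.

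**Conclusion.** The point holds as a cheap improvement. As written, the rule could leave an adult multisystem inflammatory case off the one output dedicated to the only named important potential risk. The gap is confined to the listing in SAP 9.2.3.2.3 and the section 10 list that uses the same definition.

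The conclusion rests on three assumptions:
- the cohort is adult, as its occupation implies;
- MedDRA 25.1 contains an adult or age-neutral PT to which such a case would be coded;
- no listed component is coded separately for the same subject.

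The number of affected subjects is assumed to be very small.

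**What to change.** Ask the coding group which multisystem inflammatory syndrome PTs MedDRA 25.1 contains. Add any adult or age-neutral PT to the list in SAP 9.2.3.2.3 and rerun that listing and the section 10 list that refers to it. Mark the term as added after data fixation, and state how many subjects it brings in, even if none. If there is no such PT, or if there is a reason to list only the paediatric one, a sentence in the SAP saying so settles the matter.

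The cost is a dictionary look-up, a small SAP revision after the data were fixed, and a rerun of the lists. No new data are needed.

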9.2.3.3. Information about COVID-19

Using the safety analysis set, subjects underwent or not underwent any COVID-19 pathogen test (excluding antibody test) will be summarized. Among tested subjects (except with antibody test), those with each result (positive or negative) will be summarized in terms of n and proportion. Furthermore, positive subjects will be summarized by kind of test in terms of n and proportion, and positive subjects developing COVID-19 will be summarized by n and proportion. In addition, subjects with severe COVID-19 will be summarized in terms of n and proportion (denominator = the number of subjects with COVID-19) with severe cases being defined as any of the following actions taken during the period from disease onset to the outcome date:

- Admission to an ICU
- Use of mechanical ventilation
- Use of ECMO

Subjects underwent or not underwent antibody test, as well as those with each result (positive or negative) will also be summarized in terms of n and proportion.

9.2.3.4. Subgroup analyses

Subjects with at least one serious adverse reaction will be summarized in terms of n and proportion by each factor defined in Section 5.4. According to Section 9.1.3, risk ratios between subgroups will be determined and graphically presented for the proportion of subjects with any serious adverse reactions. For all factors except sex and age, risk ratios adjusted for sex and age (<65 yrs., ≥65 yrs.) will also be determined using the Mantel-Haenszel method, and graphically presented. If there is a category with only <5 subjects and recategorization has been determined to be infeasible after consideration, however, the risk ratio for such category may not be determined.

For each of the following factors among specified in Section 5.4, subjects who had serious adverse reactions will be summarized by SOC and PT in terms of n and proportion.

- Age [<65 yrs., ≥65 yrs.]
- Pregnancy (women only) [absent, present]
- Renal impairment [absent, present]
- Hepatic impairment [absent, present]

Serious adverse events will also be analyzed in the same manner.

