#### **8.7.2. Safety analyses**

Serious adverse events entered in the CRF submitted by the investigator for which the causal relationship with this product cannot be ruled out will be handled as serious adverse reactions, and the number and proportion of subjects with serious adverse reactions ([%]: number of patients with adverse reactions/number of subjects included in safety analysis) will be tabulated. Exploratory analyses will be performed as needed.

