2.1. Study Design

[Vaccination Recipients Included in this Study]

Subjects must meet all of the following inclusion criteria to be eligible for inclusion in this study:

- Subjects who participated in the Investigation of Health Status of Recipients Vaccinated First and have provided written informed consent to continued participation in this study.

[Exclusion Criteria]

There are no exclusion criteria for this study.

[Safety Evaluation Period]

Subjects in this study will be followed for 11 months from the day following 28 days after the final vaccination of the initial immunization with this product (i.e., the end of the observation period in Investigation of Health Status of Recipients Vaccinated First).

Subjects who discontinued this study will be followed until the day of discontinuation, and those who received booster vaccination (regardless of whether it is with this product or not) will be followed until the day before the booster vaccination.

[Planned Study Period]

The planned period covered by this study is as follows.

- Investigation period: From the day following the day of completion of the observation period for the first subject who has completed the observation period in the Investigation of Health Status of Recipients Vaccinated First to the end of the observation period for the last subject investigated in this study (scheduled from March 2021 to August 2022)

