8. HANDLING OF DATA WITH MISSING INFORMATION ON BOOSTER (THIRD) VACCINATION

If for a subject it cannot be determined whether booster (third) vaccination was given or not or although booster vaccination was confirmed to have been given but its date is unknown, the subject's data covered by CRF Booklet 02 (i.e., data from the day following 6 months after the final vaccination with this product for the initial immunization to 12 months [52 weeks] following the final vaccination with this product for the initial immunization) will be excluded from the safety analysis. Data excluded should be those from the next day of completion (termination) of observation (final observation day) for CRF Booklet 01 (or for data lacking information of date, data collected in CRF Booklet 02 should be excluded), and a separate list of excluded data will be prepared.

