9.1.3. Binary variables

For binary variables, subjects included in each binary category will be calculated in terms of frequency and proportion. When a confidence interval (CI) is determined for a proportion, the two-sided 95% CI (exact method) will be determined.

When a comparison for proportion is made between subgroups, the risk ratio and its 95% CI will be calculated. They will also be presented graphically (See Appendix 1).

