9.2.2. Subject characteristics and treatment history

9.2.2.1. Subject characteristics

Using the safety analysis set, characteristics of vaccinated subjects collected in the Investigation of Health Status of Recipients Vaccinated First will be summarized according to Section 8.1, with respect to the following factors:

- Sex [male, female]
- Age (continuous)

- Age (categorical) [≥ 0 to <10 yrs., ≥ 10 to <20 yrs., ≥ 20 to <30 yrs., ≥ 30 to <40 yrs., ≥ 40 to <50 yrs., ≥ 50 to <60 yrs., ≥ 60 to <70 yrs., ≥ 70 to <80 yrs., ≥ 80 to <90 yrs., ≥ 90 yrs.]
- Past history [absent, present]
- Complications [absent, present]
- Allergy [absent, present]
- Suspected pregnancy/Lactation (women only, for each dose number for initial immunization) [absent, present]
- Pregnancy (women only) [absent, present]
- Lactation (women only) [absent, present]
- Duration of safety assessment (days)
- Number of doses for initial immunization during the study period for the Investigation of Health Status of Recipients Vaccinated First [1 dose, 2 doses]
- Dose interval for initial immunization (recipients of two doses only) (day of 2nd dose – day of 1st dose)
- Booster (third) vaccination [absent, present (this product, other), unknown]

Using the safety analysis set, a breakdown of subjects according to each of the following factors will be presented in terms of n and proportion by system organ class (SOC) and preferred term (PT):

- Past history
- Complications

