9.2.3.1.3. Onset time of serious adverse reactions

Serious adverse reactions will be summarized in terms of n and proportion (denominator = the number of subjects vaccinated) by the time of first onset [from the day after 28 days following the last dose for initial immunization with this product to 3 months after the last dose for initial immunization with this product, from the day after 3 months following the last dose for initial immunization with this product to 6 months after the last dose for initial immunization with this product, from the day after 6 months following the last dose for initial immunization with this product to 12 months after the last dose for initial immunization with this product] and by SOC and PT. For subjects with booster vaccination, only events that occurred by the day before booster dosing will be included.

9.2.3.1.4. Occurrence of serious adverse reactions in subjects excluded from the safety analysis set

Using data from CRF-collected subjects, serious adverse reactions reported during the entire evaluation period in subjects excluded from the safety analysis set will be identified and presented in tabular form. The adverse reactions identified will also be summarized in terms of n by SOC and PT.

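### The subgroup risk ratios take no account of unequal follow-up, so they can show a false excess or a false deficit if follow-up differs between categories; person-time should be reported beside them.

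*SAP*

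**What the plan says.** **Measure.** SAP 9.1.3: "When a comparison for proportion is made between subgroups, the risk ratio and its 95% CI will be calculated". SAP 9.2.3.4 applies this to the factors in SAP 5.4: "risk ratios between subgroups will be determined and graphically presented for the proportion of subjects with any serious adverse reactions". The same section extends it to serious adverse events. Protocol 8.7.2 defines the proportion as "number of patients with adverse reactions/number of subjects included in safety analysis", so the denominator is a count of subjects.

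**Follow-up.** SAP 2.1 ends the safety evaluation period early for two groups. For boosted subjects, "those who received booster vaccination (regardless of whether it is with this product or not) will be followed until the day before the booster vaccination". For dropouts, "Subjects who discontinued this study will be followed until the day of discontinuation". SAP 8 adds a third cut when booster status or date is unknown: "Data excluded should be those from the next day of completion (termination) of observation (final observation day) for CRF Booklet 01". That is not among the reasons in SAP 5.1 for leaving the safety analysis set, so such a subject still counts as one in the denominator. SAP 9.2.3.4 does not restate the booster cut. It follows from SAP 2.1 and is explicit for the onset-time tables (SAP 9.2.3.1.3: "For subjects with booster vaccination, only events that occurred by the day before booster dosing will be included").

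**Adjustment.** All factors except sex and age also get a Mantel-Haenszel risk ratio, stratified by sex and by age below 65 versus 65 and over. The duration of safety assessment and booster status are summarised for the whole safety analysis set (SAP 9.2.2.1) and enter no comparison. No person-time rate, common window or follow-up sensitivity analysis is specified, and the limitations in Protocol 8.9 do not mention unequal follow-up.

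**The concern.** A subject boosted at month 8 contributes about 7 months of counted time and an unboosted subject about 11, yet both add one to the denominator. A category whose members are boosted later or less often has more time in which an event can be counted. A category boosted earlier, or with more unknown booster dates, has less. The first could show an apparent excess, and in the second a real signal could be hidden.

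These ratios are the plan's only between-group comparisons of safety. They are graphed and form part of the final analysis that supports re-examination (SAP 3). Booster timing could plausibly vary with age, pregnancy or illness, which are among the factors compared. With no hypothesis tests planned, the risk is a misleading ratio and graph rather than an inflated error rate.

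**Working it through.** **1. Confirm what the planned ratio is.** SAP Appendix 1 gives a mock sex contrast of 18/2220 versus 3/1099, RR 2.97 (0.88 to 10.06).
- RR = (18/2220)/(3/1099) = 2.97.
- SE of log RR = √(1/18 − 1/2220 + 1/3 − 1/1099) = 0.6225, and exp(1.96 × 0.6225) = 3.39.
- Limits: 2.97/3.39 = 0.88 and 2.97 × 3.39 = 10.06.

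All nine computable rows reproduce, apart from one upper limit that differs by rounding (7.75 against 7.74). The planned measure is a plain ratio of head-count proportions.

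**2. Follow-up limits (Protocol 8.2.6, SAP 8).** Full follow-up runs from day 29 to week 52: 364 − 28 = 336 days. The nominal Booklet 01 period runs to week 24: 168 − 28 = 140 days.

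**3. Null ratio under a constant rate.** With the same low event rate in both categories, the expected proportion is nearly proportional to observed time, so the null risk ratio is about the ratio of mean observed times. Assumptions, not in the documents: booster at month *b*, a fraction *f* unboosted to month 12, and a start at 28/30.4 = 0.92 months.

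Mean months = *f*(12 − 0.92) + (1 − *f*)(*b* − 0.92)

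| Unboosted, category vs reference | b = 8 | b = 9 | b = 10 |
|---|---|---|---|
| 30% vs 10% | 8.28/7.48 = 1.11 | 8.98/8.38 = 1.07 | 9.68/9.28 = 1.04 |
| 50% vs 10% | 9.08/7.48 = 1.21 | 9.58/8.38 = 1.14 | 10.08/9.28 = 1.09 |
| 80% vs 10% | 10.28/7.48 = 1.37 | 10.48/8.38 = 1.25 | 10.68/9.28 = 1.15 |

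With the same *f* and *b* in both categories the ratio is 1.00. The outer bound from the booklet limits is 336/140 = 2.40. It would need every subject in one category to be cut at week 24 and none in the other to be cut at all, so it is a limit and not an expectation.

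**4. Rate not constant.** If one category is fully followed, the other is cut, and a share *s* of full-window events falls in the extra time, the null ratio is 1/(1 − *s*): 1.00 at *s* = 0, 1.11 at *s* = 0.10 and 1.49 at *s* = 0.33.

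**5. Does Mantel-Haenszel help?** Illustrative strata (men <65, women <65, men ≥65, women ≥65):
- category sizes 300, 400, 200, 100
- reference sizes 5,700, 11,600, 1,000, 700
- expected events per subject over 336 days 0.008, 0.006, 0.02, 0.016, equal in both categories.

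Expected proportion = 1 − exp(−rate × days).
- Follow-up of 308 versus 224 days within every stratum: crude RR 1.85, Mantel-Haenszel RR 1.37, follow-up ratio 308/224 = 1.375. The adjustment removes the sex/age confounding and leaves the follow-up effect. A Mantel-Haenszel rate ratio on person-time gives 1.00.
- Follow-up differing only by age stratum (224 days below 65, 308 at 65 and over): Mantel-Haenszel RR 1.00.

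**6. Does a rate ratio always help?** Take *b* = 8, 50% versus 10% unboosted, and all events before month 8. The planned risk ratio is 1.00, which is right. The rate ratio is 7.48/9.08 = 0.82, a false deficit, because the category with more unboosted subjects is diluted with event-free time.

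**The case against.** A reader might infer that a later-boosted subgroup will show a false excess that the adjustment cannot remove, and that interpretation should move to a rate ratio. The documents do not support this.

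- **The bias is conditional.** It needs follow-up to differ between categories and events to occur in the extra time. The documents give no booster timing, and the cohort is one occupational group. The wider contrasts above, such as 80% versus 10%, have no basis in the text.
- **The adjustment is not useless.** Mantel-Haenszel removes follow-up differences that run only through sex or the 65-year cut. Differences within strata remain, as do any for the sex and age factors, which get no adjustment.
- **Reactions may cluster early.** A serious adverse reaction is an event whose causal link to the product cannot be ruled out (Protocol 8.7.2). If most arise before the booster, the planned ratio is close to right and the rate ratio is the biased one (step 6).
- **Scope and consequence are limited.** SAP 5.4 makes only sex, age and allergy history routine. The pregnancy, lactation, renal and hepatic factors are analysed if needed. SAP 4 sets no tests or decision rules, and follow-up and booster status are at least summarised overall.

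All four points stand, and they limit how strongly the concern can be put. None of them shows that follow-up is balanced between categories or gives a reader of the planned tables a way to check. SAP 9.2.3.5 allows further analyses, but it specifies none and reports them only if they prove important to interpretation.

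**Conclusion.** The concern holds in conditional form. The planned subgroup ratios mix event risk with length of observation, and nothing in the plan shows how much of a ratio comes from the latter. The direction can be either way. Under a constant rate and the assumed booster patterns the null ratio runs from 1.04 to 1.37. It is 1.00 if follow-up is equal between categories, or if all events precede the booster. The constant-rate figures are more credible for serious adverse events than for serious adverse reactions. It has not been shown that the ratios will be biased, or that a rate ratio is the better sole basis for interpretation. What is justified is a low-cost addition that makes any difference in follow-up visible.

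**What to change.** In SAP 9.2.3.4, separately for serious adverse reactions and serious adverse events:

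1. For each category of each factor analysed, report the duration of safety assessment and the person-years, cut at first event.
2. Keep the planned risk ratios. Beside them, add as supplementary or sensitivity analyses (a) the incidence rate ratio of first event with 95% CI, crude and Mantel-Haenszel over the same sex/age strata, and (b) a risk ratio restricted to a common window such as day 29 to week 24, counting only events in that window.
3. State that a subgroup difference is read with caution where these measures disagree, and that the additions are reported whatever they show.
4. State two limits. The rate ratio assumes a roughly constant rate. For pregnancy and lactation, recorded as present or absent at any time in the observation period (Protocol 8.3.2), whole-subject person-time does not resolve the time-varying classification.

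The cost is a few table columns and a small derivation from dates already collected, because the duration in SAP 9.2.2.1 is not stated to be cut at first event. No new data are needed. The common window discards later events, and subjects who are boosted or drop out before week 24 are still short of it. The SAP revision history marks versions 5.0 and 6.0 as written with all data fixed, so the additions must be labelled as made after that point.
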